Appendix 2.2. Endpoint Derivations

Appendix 2.2.1. % Liver Fat using MRI-PDFF and CCI

For each participant in the Imaging substudy population, the Whole Liver PDFF (WLPDFF in %) will be calculated from the pre-defined individual segmental PDFF (SPDFF in %) measured in Segment I, II, III, IVa, IVb, V, VI, VII and VIII as follows:

[figure not shown]
WLPDFF= (SPDFFSegment II + SPDFFSegment III + SPDFFSegment IVa+ SPDFFSegment IVb + SPDFFSegment VI + SPDFFSegment VII + SPDFFSegment VIII + (0.36 * SPDFFSegment I)) / 8.36 (if all segments are assessed and not missing/mapping at Baseline, and on Week 6, Week 24, and Week 48).

Note: If data for all segments is not included, then adjust the denominator accordingly. This should be the number of all segments contributing to the numerator, except if this includes Segment 1, then add 0.36 instead of 1). For example, if the only segment not included is Segment 1 then the denominator=8, if segment 2 is not included then the denominator=7.36 ((7 x 1)+0.36) etc.

[figure not shown]
Calculation Rule for % Liver Fat when Assessed with MRI-PDFF:

WLPDFF will be calculated on mapping non-missing segments at Baseline, and at Week 6, Week 24, and Week 48.

For instance, if results are reported for all segments at Baseline, and at Week 6, Week 24, and Week 48 (see below), the number of segments assessed is equal to 9.

If at Baseline, all segment data are available but, at Week 6, or Week 24, or Week 48, only 7 segments have results reported, WLPDFF will be calculated at Baseline, and at Week 6, Week 24, and Week 48 and using the matching individual segments providing values on all weeks. For instance, based on the schema below, segment II and Segment V will not be used to calculate WLPDFF on any of the time points reported. In this case, WLPDFF will be calculated using data in the 7 segments reported at all non-missing visits. A minimum of 5 segments need to be available at Baseline and at least one post-baseline visit in order to calculate WLPDFF and the participant should have a fasted status of 'Yes' (i.e. fasted for a duration of at least 4 hours). If a visit has fewer than 5 segments or the participant was not fasted, then the whole visit would be considered 'missing'.

WLPDFF and individual % liver fat measured in each individual segment will be included in source data. WLPDFF will be summarized by randomized arm and Week.

Note: If baseline at the individual segment level is zero by itself or after imputation, % change from baseline and relative change at individual segment level will be reported as "." (because not calculable) with a footnote explaining that the value at baseline was zero or imputed to zero.

A similar derivation will be utilized to determine (values of which will be provided for each segment), which reflects the presence of reflective of (combination of liver and column).

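### SAP Appendix 2.2.1: the complete-data whole-liver fat formula, as the text reads, omits Segment V but divides by 8.36, so absolute levels (not percent change) would be about 12% too low if coded literally

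*SAP*

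**What the plan says.** SAP Appendix 2.2.1 derives WLPDFF from segmental values "measured in Segment I, II, III, IVa, IVb, V, VI, VII and VIII as follows". That is nine segments, with V among them.

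The formula begins "WLPDFF= (SPDFFSegment II + SPDFFSegment III + SPDFFSegment IVa+ SPDFFSegment IVb + SPDFFSegment VI" and, from IVa to its end, reads "SPDFFSegment IVa+ SPDFFSegment IVb + SPDFFSegment VI + SPDFFSegment VII + SPDFFSegment VIII + (0.36 * SPDFFSegment I)) / 8.36". It is stated to apply "if all segments are assessed and not missing/mapping at Baseline, and on Week 6, Week 24, and Week 48", that is, to complete data.

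A note then gives the divisor when some segments are not included: "This should be the number of all segments contributing to the numerator, except if this includes Segment 1, then add 0.36 instead of 1". Two worked cases follow: "if the only segment not included is Segment 1 then the denominator=8", and "if segment 2 is not included then the denominator=7.36 ((7 x 1)+0.36".

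The calculation rule further down the appendix counts complete data as nine segments. Its example of incomplete data sets aside Segments II and V at every time point because they were not reported at every visit. Segment V is therefore an ordinary contributor, dropped only when it is missing.

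WLPDFF feeds the liver-fat secondary endpoint (SAP Sections 2.1.2, Estimand 2.5, and 6.2.5). Section 6.2.5.1 analyses the log of the post-baseline to baseline ratio with log baseline liver fat as a covariate. It also presents observed liver fat and absolute change by arm.

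**The concern.** The formula line disagrees with everything around it. The list, the divisor 8.36, both worked divisors, the count of nine and the incomplete-data example all need Segment V at full weight. Only the numerator leaves it out. No statement in the SAP or protocol says that V is excluded by design.

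A programmer who copied the line would produce a quantity that is not a weighted mean: its weights add to less than its divisor. Four outputs would be touched:

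- **Levels.** Observed liver fat at baseline and later visits, and absolute change, would be scaled down for complete cases.
- **Comparability.** A participant without Segment V, handled by the note, would get a proper mean over the remaining segments. A participant with all nine would not. The reported level would then depend on which segments were readable.
- **Covariate.** Log baseline liver fat would carry that difference into the ANCOVA and the repeated-measures model.
- **Percent change.** Segment V's own response would never count.

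The appendix also says that a second segment-based MRI measure (its name is redacted) will be derived in a similar way, so the slip could be copied there.

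**Working it through.** **Inputs, all from SAP Appendix 2.2.1.** Weight 1 for each of II, III, IVa, IVb, V, VI, VII and VIII; weight 0.36 for I; printed divisor 8.36; worked divisors 8 (without I) and 7.36 (without II).

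**Step 1: reproduce the plan's own figures with V included.**

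- All nine segments: 8 × 1 + 0.36 = 8.36, as printed.
- Without Segment I: 8 × 1 = 8, as printed.
- Without Segment II: 7 × 1 + 0.36 = 7.36, as printed.

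All three need V as a full-weight term.

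**Step 2: sum the weights in the numerator as it reads.** II, III, IVa, IVb, VI, VII and VIII give 7, and Segment I gives 0.36, so the total is 7.36. Under the note's own rule, that numerator would take a divisor of 7.36.

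**Step 3: size of the error in the level.** The literal result falls short of the intended one by SPDFF_V / 8.36. With r = SPDFF_V / WLPDFF, the relative shortfall is r / 8.36. The documents give no segment-level values, so r is an assumption:

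| r (assumed) | Relative shortfall |
|---|---|
| 0.8 | 0.8 / 8.36 = 9.6% |
| 1.0 | 1.0 / 8.36 = 12.0% |
| 1.2 | 1.2 / 8.36 = 14.4% |

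At r = 1 the ratio is 7.36 / 8.36 = 0.880. A liver with uniform 20% fat is reported as 20 × 0.880 = 17.6%.

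**Step 4: dependence on which segment is missing.** Take the literal numerator with the note's divisors, and uniform fat:

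| Data | Literal weights / divisor | Ratio to the true level |
|---|---|---|
| Complete | 7.36 / 8.36 | 0.880 |
| I missing | 7 / 8 | 0.875 |
| II missing | 6.36 / 7.36 | 0.864 |
| V missing | 7.36 / 7.36 | 1.000 |

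**Step 5: percent change.** The same segments are used at all of a participant's visits.

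- *Uniform fat, 20% falling to 12%.* Intended: 12 / 20 − 1 = −40.0%. Literal: (12 × 0.880) / (20 × 0.880) − 1 = −40.0%. The factor cancels.
- *Segment V responds differently.* Every segment starts at 20%. At follow-up, V is 0.8 times the others (9.6% against 12%). Intended: (7.36 × 12 + 9.6) / (8.36 × 20) − 1 = 97.92 / 167.2 − 1 = −41.4%. Literal: −40.0%.
- *V at 1.2 times the others (14.4%).* Intended: (88.32 + 14.4) / 167.2 − 1 = −38.6%. Literal: −40.0%.

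The loss is about 1.4 percentage points in either direction in these assumed cases, and zero if V moves with the rest.

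**Step 6: covariate.** For complete cases with r = 1, log baseline shifts by ln(0.880) = −0.127. If every participant were complete, this constant would go into the intercept. It matters only when complete and incomplete cases are mixed, and the documents give no figure for that mix.

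**The case against.** The strongest reply is that the SAP itself may contain no error. The text at hand was read from the PDF by a program, and the same reading loses short runs elsewhere. The secondary objective on responder definitions is garbled in the protocol Synopsis but whole in protocol Section 3. Section 3 in turn lacks the two-stage fibrosis item that the Synopsis lists among the similar estimands. The minus sign in the percent-change formula is present in SAP Section 5.2.2 but gone in Sections 6.2.5.1 and 6.3.6.1. A run of near-identical segment terms is an easy place to lose one. This stands as a live explanation. Against it, the formula's brackets balance, its other eight terms and its divisor are present, and no gap or redaction mark lies between IVb and VI. The documents alone cannot settle the matter.

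A second reply is that the intended formula can be recovered from the rest of the appendix, so a careful programmer would restore V. That also stands. It lowers the risk, but a derivation rule should not need repair by its reader.

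A third reply concerns reach. A reader might infer that the liver-fat secondary endpoint or its treatment effect is biased by 12%. The documents do not support this. The endpoint is a within-participant ratio on matched segments, so the scale factor cancels, as Step 5 shows. Nor do they support reading the omission as a deliberate exclusion of Segment V.

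**Conclusion.** The text of SAP Appendix 2.2.1 contradicts itself: the numerator weights are 7.36, the divisor is 8.36, and every other statement in the appendix requires Segment V. The consequence is conditional on the line being coded as it reads. In that case, absolute liver-fat levels in complete cases would be about 12% too low in relative terms. This is exact only if Segment V equals the whole-liver mean, and the shortfall is 9.6% to 14.4% over the assumed range. Levels would also not be comparable with those of participants whose Segment V is missing.

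The effect is confined to the level and absolute-change summaries in the imaging substudy, to the log-baseline covariate when complete and incomplete cases are mixed, and to Segment V's own contribution to percent change. No 12% bias in the percent-change endpoint follows, and the primary biopsy endpoint does not use WLPDFF. This is a minor point: a line to verify and, if needed, to correct.

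**What to change.** 1. Compare the formula line with the source SAP and with the programming specification for WLPDFF. If both contain Segment V, nothing more is needed.
2. If V is absent, write the complete-data formula as (II + III + IVa + IVb + V + VI + VII + VIII + 0.36 × I) / 8.36. The divisor, the note and the worked examples stay as they are.
3. Apply the same check and correction to the second segment-based MRI measure at the end of Appendix 2.2.1.
4. As a programming test, feed in a uniform liver: equal values in all segments must return that value, with complete data and with any one segment missing.

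The cost is one term in the SAP and a short check of the code. Design, data collection and the analysis models do not change.

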Appendix 2.2.2. MRI-derived Liver Volume

No additional derivation is required for MRI-derived Liver Volume – a single value (per participant per visit) for liver volume (in mL) will be recorded on the database.

Appendix 2.2.3. MRI-derived

No additional derivation is required for MRI-derived CCI — a single value (per participant per visit) for CCI — (in mL) will be recorded on the database.

Appendix 2.2.4. Fasting Plasma Glucose and Fasting Plasma Insulin (T2DM Participants Only)

FPG and FPI values will be assessed at timepoints described in the Schedule of Activity of the protocol.

Note: if plasma glucose concentrations are reported in mmol/L, transform the value in mg/dL using the following equation:

Glucose (mg/dL) = 18 * Glucose (mmol/L)

Appendix 2.2.5. Homeostatic Model Assessment for Insulin Resistance (T2DM Participants Only)

The HOMA-IR will be derived using fasting plasma glucose values and fasting plasma insulin values at timepoints described in the Schedule of Activity of the protocol. The formula used to derive HOMA-IR is as follows:

HOMA-IR = (Glucose_{Fasting Concentration} x Insulin_{Fasting Concentration}) / 405

where plasma glucose concentrations is reported in mg/dL and plasma insulin is reported in mU/L. As such, HOMA-IR is unit-less.

DMB02-GSOP-RF02 5.0 Statistical Analysis Plan Template 05-Dec-2019
PFIZER CONFIDENTIAL
Page 71
TMF Doc ID: 98.03

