In this study, based on a combination of thorough medical history (including assessment of ethanol intake and administration of the interview-version of the AUDIT 10-item questionnaire 18), and clinical laboratory tests (including GGT and %CDT), medically-qualified site-staff will be required to rule-out alcohol-based as well as other causes of hepatic steatosis/inflammation/fibrosis, and ensure that the population enrolled is confirmed, as best as possible, to have NASH with F2-F3 liver fibrosis. 19 These assessments (AUDIT and %CDT) will be re-assessed prior to randomization and at end of dosing to confirm that while in the study alcohol intake remained in moderation. Participants with previously confirmed genetic polymorphisms, for example, PNPLA3 carriers, are eligible given these polymorphisms are known to modify/increase risk for steatohepatitis but do not by themselves cause steatohepatitis.

inclusion/exclusion criteria have been defined to help limit pharmacokinetic variability while also capturing a population that is characteristic of the intended target population. Blood samples (both pre- and post-dose) to permit population-pharmacokinetic analysis will be collected to further examine the effect of demographics on pharmacokinetic variability.

A priori, to permit an evaluation of potential differences in treatment response in NASH with F2 versus NASH with F3 fibrosis with DGAT2i and DGAT2i + ACCi, this study employs stratification based on degree of fibrosis (F2 vs F3). In addition, this study will identify the population with and without a diagnosis of T2DM based on HbA1C result ≥6.5% and/or current use of approved agents for glycemic control (Section 6.5.1). This is to permit an assessment of whether DGAT2i and/or DGAT2i + ACCi demonstrate insulin sensitization properties similar to the effect observed with ACCi alone in the 16-week, Phase 2a study in participants with NAFLD.

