6.5.1. Medication for Glycemic Control

Participants are permitted to be on stable doses of up to a maximum of 3 agents for glycemic control, for \geq 12 weeks prior to SCR1 and until 1st on-site Follow-up/Visit 20, across the country-specific approved classes of agents for glycemic control (eg, biguanides, DPPIV inhibitors, SGLT2 inhibitors, sulphonylureas, α -glucosidase inhibitors, meglitinide analogues);

 Those on thiazolidinediones/PPARγ (eg, pioglitazone) must be on a stable dose for ≥24 weeks before SCR1;

- Those on metformin at doses >1 gm/day will need to agree to decrease the dose by
 one-third or one-half (guided by available tablet strengths) starting at an on-site
 Visit 3/Run-In conducted after confirmation of eligibility on SCR2 liver biopsy, with
 upward adjustment in metformin dose permitted post randomization based on FPG
 results refer to Appendix 10;
 - Including once double-blind, double-dummy study intervention is stopped;
- Those on insulin must be on stable doses for ≥12 weeks before SCR1;
 - Short term use of sliding scale insulin to manage glycemic control during a concomitant acute medical condition is acceptable so long as participant is medically stable at SCR1;
- Those on GLP1r agonists must be on stable doses for ≥12 weeks before SCR1.

In order to ensure appropriate glycemic control, per local/in-country standard-of-care, and considering the duration of dosing with study intervention (ie, 48 weeks), it may be necessary to adjust the dose(s) of agents for glycemic control post randomization – refer to Appendix 10 for sponsor-suggested guidance.

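### The exploratory fasting-insulin and HOMA-IR analyses include participants on injected insulin, in whom HOMA-IR does not validly measure insulin resistance

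*SAP*

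**What the plan says.** **Who may enrol.** Protocol Section 6.5.1 accepts insulin users: "Those on insulin must be on stable doses for ≥12 weeks before SCR1". It adds that "Short term use of sliding scale insulin to manage glycemic control during a concomitant acute medical condition is acceptable", provided the participant is medically stable at SCR1. Glycaemic agents are meant to stay stable until the first on-site follow-up, but the same section foresees that "it may be necessary to adjust the dose(s) of agents for glycemic control post randomization".

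**Who counts as T2DM.** Protocol Section 4.2 defines T2DM by HbA1C of at least 6.5%, by current use of approved glucose-lowering agents, or by both. Any insulin user therefore meets the definition. The stated purpose is to see whether the study drugs "demonstrate insulin sensitization properties similar to the effect observed with ACCi alone".

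**What is derived.** SAP Appendix 2.2.5: "The HOMA-IR will be derived using fasting plasma glucose values and fasting plasma insulin values". The product is divided by 405, "where plasma glucose concentrations is reported in mg/dL and plasma insulin is reported in mU/L".

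**What is analysed.** SAP Sections 3.3 and 6.3.6 list change from baseline in FPI and HOMA-IR for all participants and again for T2DM only. Section 6.3.6.1 fits an MMRM to all observed post-baseline data, with treatment, week, their interaction, baseline fibrosis stage and baseline value. There is no term or rule for insulin use. The validity rules for these samples are collection before the morning study dose and an overnight fast of at least 8 hours (SAP Section 3.5.2).

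**The concern.** HOMA-IR infers resistance from how much of a person's own insulin accompanies a given fasting glucose. In someone injecting insulin, the glucose is partly set by the dose. The measured insulin may partly be the dose as well, depending on whether the assay detects the product. The index can then move because the dose moved, with no change in sensitivity. This follows from the structure of the formula; the documents do not discuss it.

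At stake is the reading of the insulin-sensitization question in the T2DM subset, where every insulin user sits. HOMA-IR is the listed endpoint aimed most directly at that question. The SAP already sets wrongly fasted samples to missing because they do not measure what is intended (Section 5.3). Values from insulin users raise the same kind of validity problem and have no rule.

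**Working it through.** **1. The formula.** SAP Appendix 2.2.4 converts glucose from mmol/L to mg/dL with a factor of 18. Then 405 / 18 = 22.5, the usual constant for glucose in mmol/L. The formula is correct; the issue is whom it is applied to.

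**2. Effect on the level.** HOMA-IR is linear in measured insulin. If a share s of measured insulin is injected, the index is inflated by 1 / (1 − s):

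| s (assumed) | Inflation |
|---|---|
| 10% | 1.11 |
| 25% | 1.33 |
| 50% | 2.0 |
| 75% | 4.0 |

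Take assumed values of glucose 140 mg/dL and own insulin 20 mU/L. HOMA-IR is 140 × 20 / 405 = 6.9. With 20 mU/L of detected injected insulin it is 140 × 40 / 405 = 13.8.

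**3. What survives in change from baseline.** Write x for a constant injected contribution, and g₀ and g₁ for glucose at the two visits. Its contribution to the change is x(g₁ − g₀) / 405.
- Glucose unchanged: the contribution is zero, so a constant x cancels.
- Glucose falls from 150 to 140 with x = 20: 20 × (−10) / 405 = −0.49. Cancellation is incomplete.
- Injected contribution changes by d at constant glucose g: the term is g × d / 405, and none of it cancels.

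**4. Noise.** Assume the change in HOMA-IR has SD 3 in non-users. Let a proportion p be users, with an independent mean-zero change in injected insulin of SD D mU/L, at glucose 140. The variance ratio against no users is 1 + p × (140 × D / 405)² / 3². For p = 0.10 and D = 20: 140 × 20 / 405 = 6.91; 6.91² = 47.8; 1 + 0.10 × 47.8 / 9 = 1.53.

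| p | D = 10 | D = 20 | D = 40 |
|---|---|---|---|
| 5% | 1.07 | 1.27 | 2.06 |
| 10% | 1.13 | 1.53 | 3.12 |
| 20% | 1.27 | 2.06 | 5.25 |

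Interval width scales with the square root: 1.03 times at the smallest entry (√1.07) and 2.29 times at the largest (√5.25).

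**5. One participant.** Suppose measured insulin moves from 15 to 60 mU/L at glucose 150. HOMA-IR goes from 150 × 15 / 405 = 5.6 to 150 × 60 / 405 = 22.2, a change of 16.7. With an assumed 25 to 35 T2DM participants per arm, this shifts the raw arm mean by 16.7 / 35 = 0.5 to 16.7 / 25 = 0.7. Someone at 60 mU/L at both visits with unchanged glucose contributes zero.

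Steps 2 to 5 are illustrations. The documents give neither p, s, D, the SD nor the T2DM count, and they do not describe the insulin assay.

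**The case against.** The plan already contains several protections:
- Insulin must be stable before entry, and glycaemic agents are intended to stay stable through treatment.
- Participants come to visits fasted and before their morning glucose-lowering medication (Protocol Section 5.4.2).
- The endpoint is change from baseline with the baseline value in the model, so a constant injected contribution is partly absorbed.
- SAP Section 5.2.2 allows a transformation or non-parametric analysis if model assumptions fail badly. Section 6.3.6.1 adds medians and box plots.
- Changes in glycaemic medication are tabulated (SAP Sections 3.5.3 and 6.5.5).
- The endpoints are exploratory, no hypothesis tests are planned, and HbA1c, FPG and adiponectin also bear on the glycaemic question.

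All of this stands, and it reduces the problem without removing it. The visit instructions do not address evening or long-acting insulin. Dose changes are foreseen. For HOMA-IR, log transformation is a contingency: Section 6.3.6.1 applies it to percentage changes, while HOMA-IR is listed as a change. Medication tables show whether treatment moved but do not repair the index.

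A reader might infer three stronger things that the documents do not support:
- **That the comparison is biased.** Randomization balances insulin users on average, and blinding is maintained. Bias needs insulin to be started or changed differently by arm, and the figure in Appendix 10 that guides such changes is not available here.
- **That a few insulin users will dominate the result.** Their number is unknown, and stable users largely cancel.
- **That measured insulin certainly includes the injected drug.** The assay is not described. If it misses a product, measured insulin no longer reflects total insulin action while glucose still does, so the index is uninterpretable for a different reason.

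**Conclusion.** The concern holds as a modest, inexpensive improvement to two exploratory parameters. As written, the SAP puts HOMA-IR values that do not measure insulin resistance, and FPI values that may include the drug, into the analyses meant to address insulin sensitization. The expected harm is added variance and loss of meaning when doses vary; bias is conditional on differential insulin changes between arms. The size is unknown. The illustrative variance ratios run from 1.07 to 5.25, entirely on the assumptions stated above. No primary or secondary endpoint is touched.

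There is also an inconsistency within the SAP. The headings of Appendices 2.2.4 and 2.2.5 limit FPG, FPI and HOMA-IR to T2DM participants, while Sections 3.3 and 6.3.6 also analyse them in everyone.

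**What to change.** Add to SAP Section 6.3.6.1, for FPI and HOMA-IR only, in both the all-participant and T2DM analyses:
- **Main analysis:** exclude participants on insulin at baseline. This is a pre-randomization characteristic, so the randomized comparison is preserved among those who remain.
- **Sensitivity analysis 1:** all participants, as now planned.
- **Sensitivity analysis 2:** additionally censor values after insulin is started post randomization. This belongs outside the main analysis, because starting insulin may itself depend on worsening glycaemia and the analysis assumes missing at random.
- **FPG and HbA1c:** make no exclusion for insulin use.

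In the same edit, align the headings of Appendices 2.2.4 and 2.2.5 with Sections 3.3 and 6.3.6.

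No new data are needed. Protocol Section 6.5 requires daily dose and start and stop dates for glycaemic agents, and SAP Section 3.5.3 names the anti-diabetic CRF page. The cost is a few lines of SAP text and a smaller n for two exploratory parameters. Patient management does not change.
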